### **l) Withdrawal of Subjects**

Subjects will be withdrawn from the study if there are any intraoperative surgical complications requiring deviation from standard technique.

Subjects may withdraw from the study at any time

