### **f) Study Endpoints**

Primary study endpoints are average VAS pain score during hospitalization and postoperative narcotic usage during the hospitalization. Secondary endpoints are need for antiemetic therapy, length of hospitalization, and aggregate pain and quality of

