## Enhanced pain control after reduction mammoplasty with bupivacaine and dexamethasone regional block

life survey scores at the first post-operative visit. . Patient participation is concluded following the first post-operative visit

Patient participation will be terminated if any adverse reaction to the study medication is noted.

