### **g) Procedures Involved in the Human Research**

Study subjects will undergo breast surgery by the individual surgeon's standard technique. No changes in surgical technique will occur as part of this study. Regional nerve block with bupivacaine and/or lidocaine is typically offered to patients as part of this procedure and is considered standard of care. However, not all patients opt to receive a nerve block

For the study, subjects will be randomized to experimental and control groups in a ratio of 1:1. Randomization will occur upon enrollment in the study. When the patient is enrolled, the investigator will use the Sealed Envelope™ simple randomization tool to assign the subject a treatment group. Randomization occurs in random permuted blocks to achieve an even distribution between groups. Patients will be blinded to their study group.

All subjects will receive perineural nerve block in the preoperative holding area prior to the case performed by faculty from the anesthesia pain service. An ultrasound guided pecs block will be performed. For the block, the fascial plane separating the pectoralis major and pectoralis minor muscles is identified by ultrasound at the level of the 3rd rib. A needle is advanced into this space and the local anesthetic is infiltrated. The experimental group will receive 29cc 0.5% bupivacaine mixed with 1mL 4mg/mL dexamethasone for each side (40 cc total). The control group will receive 29cc 0.5% bupivacaine mixed with 1mL 0.9% saline solution for each side.

All patients will undergo standard breast reduction with no change in the standard operative technique.

All patients will receive a standard postoperative pain regimen as follows:

- Percocet 5/325 1 tab q4hr prn pain (moderate, 4 – 7)
- Percocet 5/325 2 tabs q4hr prn pain (severe, 8 – 10)
- IV 1mg Morphine q1hr prn breakthrough pain
- IV 4mg Zofran q8hrs prn N/V

This may be adjusted for patient drug allergies

Bupivacaine is a local analgesic used routinely during surgical procedures. It is FDA approved for this indication.

Dexamethasone is a glucocorticoid available in oral and intravenous formulations. It is FDA approved for a multitude of anti-inflammatory indications. While off label, it is standard of care to provide IV

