## Enhanced pain control after reduction mammoplasty with bupivacaine and dexamethasone regional block

Data will be extracted from the Epic electronic medical record. Consultation with medical informatics has been obtained to assist with development of an automated data collection mechanism. Data will be stored in a spreadsheet that allows for manipulation and analysis. Patient surveys will be conducted a week after the procedure and documented on paper and the responses will be manually inputted into an electronic database (REDCap). Survey responses (REDCap) will be matched to inpatient data measurements (Epic) through study ID numbers. The spreadsheet itself will be encrypted and will be stored exclusively on hospital network databases.

The two groups will be compared using a Student T test to evaluate for significant differences in the endpoints of each group.

A 2 mean 2 sided power analysis was conducted assuming the mean VAS difference between groups to be 1.5. A sample size of 30 in each group will have 81% power to detect a difference in means of 1.500 assuming that the common standard deviation is 2.000 using a two group t-test with a 0.050 two-sided significance level. We anticipate using larger numbers to power subgroup analysis.

Analysis between the two groups will involve a linear mixed effect model to compare the pain scales of the two groups over time. If vital signs are dissimilar at the beginning of the study, they will be controlled for prior to analysis. Pain medication requirement (determined by quantity of pills or mg used of same medication) will also be controlled within the analysis model. Adjustments to the pain score within the groups due to pain medication usage will be performed.

However, need for postoperative anti-emetic therapy is expected to be a somewhat rare event with similar means. In a similar power analysis with an expected group A mean of 0.5 doses and group B mean of 1 dose with standard deviation of 1, a sample size of 63 is required to reach significance. A somewhat large standard deviation is expected given the need for repeated dosing in those who do experience post-operative nausea

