### **13) Privacy and Confidentiality**

All PHI will be removed prior to storage of any patient information. PHI will not be shared with any research personnel or any other persons. Randomization status and all medications received will be disclosed to all healthcare personnel involved in the patient's care while in the hospital. The patient will not be informed of his or her study group. Patients will be completely informed of all privacy procedures as part of the consent process. Study personnel will be available to answer questions throughout the duration of the study.

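### Two rules remove patients after randomisation, one of them after the block has been given, and the plan has no all-randomised analysis or continued data collection to keep them in the comparison

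*Combined protocol and SAP*

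**What the plan says.** All references are to the combined protocol and SAP.

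- **Withdrawal rule, 10(l):** "Subjects will be withdrawn from the study if there are any intraoperative surgical complications requiring deviation from standard technique". The section does not say who decides, or what happens to the patient's data afterwards.
- **Timing, 10(g):** "Randomization will occur upon enrollment in the study", and "All subjects will receive perineural nerve block in the preoperative holding area prior to the case". The study intervention is this single preoperative block.
- **Second rule, 10(f):** "Patient participation will be terminated if any adverse reaction to the study medication is noted".
- **Outcomes, 10(f):** "Primary study endpoints are average VAS pain score during hospitalization and postoperative narcotic usage during the hospitalization".
- **Knowledge of arm:** section 13 states "Randomization status and all medications received will be disclosed to all healthcare personnel" involved in the patient's hospital care. The only blinding statement in 10(g) is "Patients will be blinded to their study group".
- **Analysis, 10(i):** t tests and a linear mixed model are named. There is no analysis population, no as-randomised rule, no follow-up of withdrawn patients and no method for their missing outcomes.
- **Sample size, 10(i):** "A sample size of 30 in each group will have 81% power". Section 10(d) expects about 60 subjects, which is 2 × 30.

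**The concern.** The order of events is randomise, block, operate, withdraw, measure pain and opioid use. The 10(l) rule therefore selects patients after treatment and before outcome. Randomisation protects the comparison only while everyone randomised stays in it.

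Three features make the selection worth closing off:

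1. The 10(l) trigger is a judgement. Section 10(g) lets each surgeon use his or her own usual technique, so there is no common yardstick for a departure from it.
2. Whoever makes that judgement may know the arm, given section 13.
3. The 10(f) rule turns on reactions to study medication. Section 11 names reactions to dexamethasone as the main added risk of taking part, so this rule can plausibly act more in one arm than in the other.

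Patients with complicated surgery may well have more pain, use more opioid and stay longer. If more of them are removed from one arm, that arm looks better than it should on every endpoint, including both primary ones.

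**Working it through.** **1. The plan's own power figure.** Inputs from 10(i): difference 1.5, SD 2.0, two-sided alpha 0.05, two-group t test, 30 per group.

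- Standardised difference: d = 1.5 / 2.0 = 0.75.
- Noncentrality: d × √(n/2) = 0.75 × √15 = 2.905, with 58 degrees of freedom.
- Power from the exact noncentral t: 81.5%. The normal approximation gives 82.8%.

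The stated 81% reproduces, so the sample-size figure is not at fault.

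**2. Power if patients are lost.** The documents give no withdrawal rate. Assume equal losses in both arms and exactly 60 enrolled.

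| Analysed per arm | Noncentrality | Power |
|---|---|---|
| 30 | 2.905 | 81.5% |
| 29 | 2.856 | 80.1% |
| 28 | 2.806 | 78.7% |
| 27 | 2.756 | 77.2% |

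Losing 1 to 3 per arm costs about 1 to 4 percentage points.

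**3. Bias if removals differ by arm.** Suppose m of the 30 patients in one arm are removed, none are removed from the other, and the removed patients average k VAS points above their own full-arm mean. The mean of those who remain falls by

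shift = m × k / (30 − m).

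Both m and k are assumptions.

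| m | k = 1 | k = 2 | k = 3 |
|---|---|---|---|
| 1 | 0.03 | 0.07 | 0.10 |
| 2 | 0.07 | 0.14 | 0.21 |
| 3 | 0.11 | 0.22 | 0.33 |

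For example, 3 × 3 / 27 = 0.33. If the excess is measured against the patients who remain, the formula is m × k / 30; for m = 2 and k = 3 that is 0.20 instead of 0.21. Against the planned 1.5, the table runs from about 2% (0.034 / 1.5) to 22% (0.333 / 1.5). Removal from the dexamethasone arm favours dexamethasone; removal from the control arm works against it.

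**4. False-positive rate in the one-sided case.** Simulation under no true effect: 30 per arm, SD 2, 10,000 trials per row. The same number of complicated patients is placed in each arm, each with 3 extra VAS points (assumed), but they are removed from one arm only.

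| Complicated per arm | Removed from one arm | Everyone kept |
|---|---|---|
| 1 | 4.6% | 3.8% |
| 2 | 5.5% | 3.6% |
| 3 | 7.0% | 3.3% |
| 4 | 9.2% | 2.9% |

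With 2 extra points instead of 3, the removal column reads 4.8%, 5.3%, 5.8% and 6.7%. The rates with everyone kept are below 5% because the simulation fixes equal numbers of complicated patients in each arm: they add to the variance but not to the difference between arms.

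**The case against.** A reader might infer that the analysis set is chosen by unblinded staff. The text does not establish that. Section 10(l) speaks of withdrawal from the study and does not say that data are discarded. It names no decision-maker. Section 13 does not say when the arm is disclosed, so the operating team's knowledge at the moment of judgement is likely but not stated. This objection stands, and the point is limited accordingly: exclusion is the natural reading of a plan with no retention rule, and unblinded judgement is possible.

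Bias also needs removals to differ by arm. The arms differ only in 1 mL of dexamethasone or saline per side, surgical technique is unchanged, and the 10(l) trigger is a surgical event. If removals are unrelated to arm, the comparison is unbiased in a narrower population. That stands for 10(l), though nothing in the plan guarantees it. It is weaker for 10(f), where the trigger is a reaction to the study medication.

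A reader might also infer that the rule takes the trial below 30 per group and below its stated power. That is not established. Section 10(d) says only approximately 60, 10(i) anticipates larger numbers (for subgroup analysis, with no figure), and 10 procedures a month over 12 months is about 120 potential patients. Even at exactly 60, the loss is small.

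Finally, the sponsor may say that complicated cases add noise. They do, but noise shared by both arms costs some precision, whereas uneven removal can shift the estimate.

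**Conclusion.** The concern holds as a gap in the analysis plan. Two rules take patients out after randomisation. The 10(l) rule does so after the block and before either primary endpoint, and nothing in 10(i) keeps these patients in the comparison. The 10(f) rule is the more plausible source of imbalance between arms.

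The likely effect is small to moderate, and its true size cannot be derived from the documents. The range of 0.03 to 0.33 VAS points assumes removal from one arm only, 1 to 3 patients, and an excess of 1 to 3 points. If complications are rare or removals are balanced, the bias is close to nil. The type I error figures describe a worst case: at 2 one-sided removals the rate is 5.5%, and it reaches 7.0% and 9.2% only at 3 and 4. Power is a secondary matter.

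The sequence of events and the absence of an all-randomised rule are certain from the text. That withdrawn patients are left out of the analysis, and that those deciding know the arm, are inferences.

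**What to change.** Change the wording in three places:

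- **10(l) and 10(f):** state that a patient who meets either rule stays in data collection. VAS scores and medication records continue to be taken from Epic, and the postoperative visit and questionnaires go ahead unless the patient withdraws consent.
- **10(i):** define the primary analysis as all randomised patients, compared by assigned arm. Report the number and reasons for withdrawals and terminations by arm.
- **10(i), sensitivity analysis:** if a set excluding technique deviations is wanted, have the deviations judged by someone unaware of the arm, and label the result as supportive only.

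Section 10(l) need not be deleted. Any clinical decision to stop study procedures for a patient is unchanged; the amendment concerns only whose data are collected and analysed.

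The cost is protocol wording. Inpatient outcomes already come from the medical record under 10(g), so little extra collection is needed. The downside is slightly more outcome variance from complicated cases.

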### **11) Risks to Subjects**

Regional nerve block is an optional component of the standardly performed breast reduction at this institution. Participation in the study does entail all the standard risks of this procedure. These are primarily bleeding or bruising at the injection site, nerve damage resulting in pain, numbness or weakness, infection, and

## Enhanced pain control after reduction mammoplasty with bupivacaine and dexamethasone regional block

inadvertent systemic injection of the anesthetic. There is a very small risk of pneumothorax.

Primary additional risk to subjects compared to the standardly practiced block is allergic or adverse reaction to the study medication posed by the administration of dexamethasone. Adverse effects of this medication include behavioral disturbance, cardiac arrhythmia, hyperglycemia, and immune suppression. There is additional risk of increased postoperative pain due to deviation from standard nerve block procedure.

### **12) Potential Benefits to Subjects**

Subjects may benefit from prolonged duration of local anesthesia resulting in enhanced postoperative pain control and decreased need for opiate analgesics.

### **13) Privacy and Confidentiality**

All PHI will be removed prior to storage of any patient information. PHI will not be shared with any research personnel or any other persons. Randomization status and all medications received will be disclosed to all healthcare personnel involved in the patient's care while in the hospital. The patient will not be informed of his or her study group. Patients will be completely informed of all privacy procedures as part of the consent process. Study personnel will be available to answer questions throughout the duration of the study.

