## Enhanced pain control after reduction mammoplasty with bupivacaine and dexamethasone regional block

dexamethasone to prevent post-operative nausea and vomiting. It has not been evaluated by the FDA as an adjunct to local anesthesia.

Pain VAS scores are routinely collected by nursing staff and entered into Epic. We will request pain evaluations at 4 hour intervals for study patients following surgery which will be entered into the Epic medical record. Medication administration is also captured in the electronic medical record. Study data will be gathered from the Epic electronic medical record.

Patients will be asked to complete the MD Anderson Brief Pain Inventory Short Form and both the Breast-Q or the SF-36 questionnaire at their first post-operative visit.

As previously stated, regional block with bupivacaine alone is routinely offered and provided to patients. Patients who do not consent to participate in the study will be offered a regional nerve block containing only bupivacaine. Anesthesia pain service faculty will perform the block regardless of study participation or study group.

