### **i) Data Management**

Prior to data collection, patients will be randomized into 2 groups (control or experimental). An independent source will generate a master list of study IDs and associated randomization status. Patients will assigned within the master list and randomized accordingly per the master list.

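### Care staff are told the treatment arm, which leaves as-needed narcotic use (a primary endpoint) open to staff-expectation bias

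*Combined protocol and SAP*

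**What the plan says.** Section 10(g) describes the blinding in one sentence: "Patients will be blinded to their study group". Section 13 repeats that the patient is not told the group. For everyone else it does the opposite: "Randomization status and all medications received will be disclosed to all healthcare personnel" who look after the patient during the admission. No section masks nurses, surgeons, anesthesia staff or whoever arranges discharge, and no section says why staff need to know the arm.

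Section 10(f) sets the endpoints: "Primary study endpoints are average VAS pain score during hospitalization and postoperative narcotic usage during the hospitalization". Need for anti-emetics and length of stay are secondary.

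The standard regimen in Section 10(g) supplies the narcotics, all as needed. Percocet is ordered in two steps by pain score, the lower being "Percocet 5/325 1 tab q4hr prn pain" for scores of 4 to 7, with two tablets for 8 to 10. The other order is "IV 1mg Morphine q1hr prn breakthrough pain", with no score attached. The anti-emetic is also as needed. On pain measurement, Section 10(g) says: "Pain VAS scores are routinely collected by nursing staff and entered into Epic".

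**The concern.** Staff who know the arm may act on what they expect of it. The protocol's own hypothesis (Abstract, Objectives, Potential Benefits) is that dexamethasone prolongs analgesia and reduces narcotic need. A nurse who knows that a patient had the active additive may be slower or quicker to offer or give an as-needed dose, may ask about pain differently, or may view readiness for discharge differently. None of this needs bad faith.

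At stake is what a difference in narcotic use would mean. It could reflect the drug, the staff's knowledge of the arm, or both. The saline additive helps to keep the patient blinded. It does nothing for endpoints that pass through the hands of staff who have been told the arm.

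**Working it through.** **Step 1. The plan's own figure.** Section 10(i) states 81% power for VAS with 30 per group, difference 1.5, SD 2 and a two-sided 0.05 t-test. The noncentrality is 1.5 / (2 × √(2/30)) = 2.90 on 58 degrees of freedom, which gives 81.5%. The figure reproduces. It depends only on sample size, difference, SD and alpha, so masking staff would change neither the sample size nor the nominal power.

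**Step 2. Where staff knowledge can enter.**

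| Endpoint | Status | Route | Check in the plan |
|---|---|---|---|
| Narcotic use | Primary | As-needed Percocet and IV morphine | Percocet dose follows score bands, but informed nurses collect the scores; morphine has no score threshold but is tied to breakthrough pain |
| Average VAS | Primary | Collected and entered by informed nurses | Patient is blinded |
| Anti-emetic need | Secondary | As-needed doses | Patient is blinded |
| Length of stay | Secondary | Discharge timing | None stated; Section 10(i) assumes means of 16 and 18 hours and describes the gap as discharge before or after midday on day 1 |

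The documents do not name who decides on an as-needed dose or on discharge. That care staff do so is an inference. They also do not say outright that the patient rates the VAS, although that is the natural reading. Section 10(g) says that medication administration is captured electronically, so the exposure lies in the decision to give a dose, not in its recording.

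**Step 3. Whether the analysis can remove it.** Let δ be the drug effect on mean narcotic use and β the difference that arises because staff know the arm. The expected difference between groups is δ + β. Section 10(i) plans a Student t-test on the endpoints and a linear mixed model for pain over time. Under the disclosure rule, staff know the arm for every patient, so their knowledge coincides exactly with the treatment indicator. Both analyses estimate δ + β, and no term in either can split the sum. More patients would not help, because β is not sampling error.

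**Step 4. Whether β can be sized.** It cannot. Section 10(i) gives an SD for VAS (2), anti-emetic doses (1) and stay (4 hours) but none for narcotic use, and nothing in the documents bears on how staff would respond. Direction is also open: extra morphine for controls would widen the narcotic difference but could narrow the VAS difference.

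**Step 5. Whether masking looks feasible.** The Abstract and Section 10(g) each give both arms the same bupivacaine volume plus a 1 mL additive. The two places disagree on that volume (19 mL against 29 cc per side) and must be reconciled, but within each the arms match. Section 10(i) already plans that "An independent source will generate a master list of study IDs and associated randomization status". The appearance of the mixtures and the identity of the preparer are not stated.

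**The case against.** The best defence is that single-blinding is an openly stated choice with plausible grounds. Section 11 lists behavioral disturbance, arrhythmia, hyperglycemia and immune suppression as dexamethasone risks, and Section 10(g) calls IV dexamethasone standard of care against postoperative nausea. Treating staff may want to know what was injected. The blinded patient's own pain also drives much of the dosing. Both points have force. The first calls for ready access to the code, but the plan does not offer it as a reason for disclosure. The second reduces the exposure without removing staff discretion.

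A reader might infer three stronger claims that the documents do not support.

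- *The bias runs chiefly through IV morphine.* Over 16 to 24 hours the orders allow at most 16 to 24 hourly morphine doses against 4 to 6 four-hourly Percocet doses. These are ceilings, not use. One is 1 mg and the other one or two tablets, with no conversion given. Percocet is not clearly protected either: a band sets the dose for a given score, and informed nurses collect the score.
- *The false-positive rate is inflated by a known amount.* With 30 per arm and no true effect, an assumed shift of 0.1, 0.25 or 0.5 SD gives rejection rates of 6.7%, 15.9% or 47.8%. The shifts are invented, and the result applies to any t-test of that size. It is no estimate for this trial.
- *The bias carries into the medication-adjusted VAS comparison.* That is possible but not shown. Adjusting pain for medication use is a separate question that would remain under full masking.

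**Conclusion.** The point holds in a limited form and should be fixed. The plan instructs that staff be told the arm while a primary endpoint consists entirely of as-needed doses and informed nurses collect the other. Narcotic use, through both drugs, is the most exposed; VAS, anti-emetic use and discharge timing are exposed to a lesser degree. The planned analyses cannot separate the resulting bias from a drug effect.

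No size or direction can be given, so the case rests on the disclosure rule and not on a calculated error rate. It assumes that care staff influence as-needed dosing and discharge. The judgement that the remedy is cheap assumes further that the two mixtures cannot be told apart by eye. Confidence is medium for these reasons.

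**What to change.** Replace the disclosure sentence in Section 13, and align Sections 10(g) and 10(i), so that:

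- the arm is known only to the person who prepares the syringe, for example existing pharmacy or block-team staff with no part in postoperative care, and to the injector only if unavoidable;
- the block is charted as bupivacaine plus a masked study additive (dexamethasone or saline) until the 1-week visit;
- staff who collect VAS, give as-needed drugs or decide discharge are not told the arm;
- treating clinicians can obtain the code on request.

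Confirm first that the two mixtures look alike. Section 10(g) has the investigator use an online "simple randomization tool to assign the subject a treatment group", while Section 10(i) describes an independent master list. Reconciling these is a separate matter, but the final wording should send each assignment only to the preparer.

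The cost is a coded record entry, a named unblinded preparer and a code-break procedure. The downside is that staff would not routinely see whether dexamethasone was given, which bears on the Section 11 risks and on IV dexamethasone use. Access to the code is therefore essential.

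If disclosure is kept, state the reason and report the staff-dependent endpoints as a limitation.
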